3.3 Tertiary/Exploratory

3.3.1 *Other Safety and Efficacy Outcomes*

1. **Global Rank:** Clinically significant events ranked in order of decreasing perceived severity. Each participant will receive a rank based upon the lowest ranking (worst) endpoint as defined in the statistical analysis plan that they experienced during the study.
2. **Events of Special Interest:** See Section 9.2.4 for a complete list of events of special interest (ESI).

4 STUDY DESIGN

Premature infants (inpatient in NICUs) will be randomized in a dose escalating approach 3:1 (sildenafil: placebo) sequentially, into each of 3 cohorts. There will be approximately 40 randomized and dosed participants in each cohort for a total of up to 120 participants.

4.1 Screening/Baseline

Research staff will document informed consent from the parent/guardian for all participants who satisfy eligibility criteria. The following information will be recorded in the case report form (eCRF) from the clinical medical record:

1. Participant demographics, including birth weight and gestational age at birth
2. Maternal race/ethnicity
3. Medical history
4. Physical examination, including actual weight
5. All mean arterial pressure (MAP) obtained in the 24 hours before the first dose
6. Concomitant medications (within 24 hours prior to start of study drug; including medications of special interest [Section 6.5.1])
7. Respiratory assessment (Section 8.2.2.3)
8. Laboratory evaluations (Section 8.2)
9. Echocardiogram: If performed per local standard of care < 14 days prior to start of study drug, a study-specific echocardiogram need not be repeated. If not performed per local standard of care < 14 days prior to start of study drug, an echocardiogram will be required to confirm eligibility.
10. Cardiac catheterization reports, if performed per local standard of care < 14 days prior to start of study drug.
11. Adverse events following informed consent (Section 9.3)

4.2 Treatment Period

The treatment period will include Days 1-28 or last day of study drug if early withdrawal of study drug. The following information will be collected and recorded while the participant is on study drug:

1. Actual weight on study Days 7 (\pm 1 day), 14 (\pm 1 day), 21 (\pm 1 day), and 28 (\pm 1 day) of study drug administration
2. Date, time, amount, and route of study drug dose
3. All concomitant medications (including medications of special interest [Section 6.5.1])
4. MAP
 - A. All MAP values obtained 24 hours after the first dose of study drug regardless of administration route.
 - B. MAP values will be obtained at a minimum at the following time points
 - i. Prior to the first dose of study drug or dose escalation: 2 hours (\pm 5 minutes), 1 hour (\pm 5 minutes), and 15 minutes (\pm 5 minutes)
 - ii. If administration route is IV:
 - a. During and following the first dose of study drug or dose escalation: MAP at start of infusion, every 15 minutes (\pm 5 minutes) during infusion, at end of infusion (inclusive of flush) (\pm 5 minutes), at 15 and 30 minutes (\pm 5 minutes) after end of infusion, hourly (\pm 15 minutes) for 4 hours, and once in the remaining 2 hours prior to the next dose.
 - b. For subsequent IV doses, the lowest valid MAP value should be recorded daily while on study drug.
 - iii. If the administration route is enteral:
 - a. During and following the first dose of study drug or dose escalation: MAP at start of enteral administration, then every 15 minutes (\pm 5 minutes) for 90 minutes (1.5 hours), then every 30 minutes (\pm 5 minutes) for 60 minutes (1 hour), then hourly (\pm 15 minutes) for 4 hours, then once in the remaining 2 hours prior to the next dose.
 - b. For subsequent enteral doses, the lowest valid MAP value should be recorded daily while on study drug.
5. Respiratory assessment, daily (Section 8.2.2.3)
6. Laboratory evaluations, at least once every 2 weeks (Section 8.2).
7. Echocardiograms and cardiac catheterization reports, if performed per local standard of care
8. PK sampling (after Day 7 [Section 8.2.2.1])
9. Adverse events (Section 9.3)

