3.2 Outcome Measures

3.2.1 Primary Outcome Measures

Safety as determined by incidence of hypotension experienced by the participants through 28 days post last dose of study drug.

Hypotension will be defined as any clinically significant low blood pressure event deemed by the treating physician to require intervention with a fluid bolus or the initiation or escalation of inotropic, vasopressor, or systemic steroid therapy with the specific intent to raise blood pressure.

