4.3 Weaning Period (Cohorts 2 and 3)

The weaning period will begin following Day 28 of study drug or, following the last day of study drug if participant was withdrawn from study drug prior to Day 28 and the dose escalated to \geq 0.5 mg/kg IV or \geq 1 mg/kg enteral.

The following information will be collected and recorded while the participant is weaning from study drug:

1. Date, time, amount and route of study drug dose
2. MAP (the lowest MAP value on last day of wean should be recorded).
3. Respiratory assessment, daily (Section 8.2.2.3)

-
4. Concomitant medications of special interest (Section 6.5.1)
 5. Echocardiogram and cardiac catheterization reports, if performed per local standard of care
 6. Adverse events (Section 9.3)

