6 STUDY INTERVENTION

6.1 Study Product Description

In the US, sildenafil, in both IV and for oral suspension, has been approved for use in other populations and for other indications by the FDA¹.

Study dosing and escalation are described in Table 3. Refer to Section 6.1.3 for study drug packaging and labeling.

Table 3 Number of Participants (N) and Dosing Scheme

Cohort ¹	Treatment Group		Sildenafil Dosing ² (mg/kg q 8 hours)		Total (N)
	Placebo (N)	Sildenafil (N)	IV	Enteral	
1	10	30	0.5	1	40
2	10	30	1	2	40
3	10	30	2	4	40

Abbreviations: IV, intravenous; N, number of participants; q, every

1 Participants will be enrolled into cohorts sequentially (i.e., Cohort 1 then Cohort 2 then Cohort 3) based on safety.

2 Route of administration, IV or enteral, is left to investigator discretion.

Dose escalations for each sequential cohort will proceed as summarized in Table 4. DSMB safety review (Section 10) will be required prior to enrolling the next cohort.

Table 4 Dose Escalations for Each Sequential Cohort

	Study Days (Dose Numbers)							
	1-2 (1-6)	3-4 (7-12)	5-6 (13-18)	7-8 (19-24)	9-10 (25-30)	11-12 (31-36)	13-14 (37-42)	15 + (43 +)
Sildenafil Dose (mg/kg)								
Cohort 1								
IV	0.25	0.5	0.5	0.5	0.5	0.5	0.5	0.5
Enteral	0.5	1	1	1	1	1	1	1
Cohort 2								
IV	0.25	0.5	0.75	1	1	1	1	1
Enteral	0.5	1	1.5	2	2	2	2	2
Cohort 3								
IV	0.25	0.5	0.75	1	1.5	1.75	2	2
Enteral	0.5	1	1.5	2	3	3.5	4	4

Abbreviation: IV, intravenous

Dose escalation will occur if the infant is:

1. Receiving exogenous oxygen or respiratory support (nasal cannula or positive pressure from any device); and
2. AST < 225 U/L and ALT < 150 U/L at last check (within 14 days) prior and closest to dose increase.

An infant will meet respiratory criteria for dose escalation only if the infant is receiving exogenous oxygen or respiratory support (nasal cannula or positive pressure from any device) for at least 12 hours before the dose escalation. Infants who do not initially qualify for escalation should be reevaluated daily to ascertain whether they meet these criteria, and escalation must occur within 24 hours of an infant meeting all dose escalation criteria (respiratory and laboratory). If escalation does not occur within this timeframe, then a protocol deviation must be recorded.

Adjusting dose for weight

The actual weight should be reviewed weekly (plus or minus one day, Section 4.2) and the dose of the study drug may be adjusted.

Weaning Period Schedule

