12.4 Final Analysis Plan

General Analysis Conventions

A comprehensive overview of planned statistical analyses will be provided in a separated statistical analysis plan.

Analysis results will be presented by placebo versus sildenafil, overall and by dose cohort. Data from participants assigned to placebo across cohorts will be pooled in result presentations.

Descriptive statistics such as number of observations, mean, median, standard deviation, minimum and maximum will be presented by treatment groups for continuous variables (such as age, weight, etc.). Other descriptive statistics such as counts, proportions, and/or percentages will be presented by group to summarize discrete variables (such as race, sex, etc.).

Participant Disposition and Study Drug Exposure

Study disposition, demographic and baseline characteristics, and study medication exposure will be summarized for the ITT Population. Study drug administration will be summarized by route (IV vs enteral), number of days of dosing, and reasons for final discontinuation of study drug.

Demographic and baseline characteristics

Demographic and baseline characteristics will include race, age, sex, and selected clinical variables recorded prior to initiation of study drug.

Safety

The primary safety endpoint is number and percent of hypotension events and will be summarized for the PP and Safety Population.

Serious adverse events will be presented overall and by each Medical Dictionary for Regulatory Activities (MedDRA) system organ class and preferred term. Severity and relationship to sildenafil or placebo will be provided.

Events of special interest will be presented overall and summarized by participant characteristics.

Prior and concomitant medications will be summarized by World Health Organization (WHO) drug class.

Laboratory data, including change from baseline, will be tabulated by treatment groups.

PK Analysis Plan

A comprehensive overview of planned PK analyses will be provided in a separated PK analysis plan.

Pharmacokinetic parameters will be estimated by population PK approach using nonlinear mixed effects modeling in NONMEM. The influence of covariates on PK parameters will be explored.

Biomarkers

We will relate the concentration of biomarkers (Section 8.2) to the development of and severity of PH in participants exposed to placebo.

Preliminary Effectiveness

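### Timed MAP series follow each dose escalation, so ascertainment of hypotension can rise with dose cohort and differ from pooled placebo; Section 12.4 should show this

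*Combined protocol and SAP*

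**What the plan says.** Section 4.2, item 4, ties intensive MAP measurement to dose changes. For IV doses: "During and following the first dose of study drug or dose escalation: MAP at start of infusion, every 15 minutes", followed by readings through to the next dose. For enteral doses: "During and following the first dose of study drug or dose escalation: MAP at start of enteral administration", with a similar timed sequence. Three readings come before each trigger ("Prior to the first dose of study drug or dose escalation: 2 hours", then 1 hour and 15 minutes). On other doses the rule is lighter: "For subsequent IV doses, the lowest valid MAP value should be recorded daily while on study drug", with the same wording for enteral doses. In weaning (Cohorts 2 and 3 only), Section 4.3 says that "the lowest MAP value on last day of wean should be recorded". Section 4.4 asks for five follow-up values in every cohort.

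The number of triggers depends on the cohort. Section 6.1 states: "Dose escalations for each sequential cohort will proceed as summarized in Table 4". That table has one dose increase in Cohort 1, three in Cohort 2 and six in Cohort 3, by either route.

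The primary outcome in Section 3.2.1 is "any clinically significant low blood pressure event deemed by the treating physician to require intervention" with fluid, inotropic, vasopressor or steroid therapy. No MAP value defines it.

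Section 12.4 states: "Analysis results will be presented by placebo versus sildenafil, overall and by dose cohort". It then pools placebo infants from all cohorts. The only sensitivity analyses planned for the primary endpoint concern siblings.

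**The concern.** An event defined by a physician's decision to treat has first to be noticed. A protocol that orders readings every 15 minutes around each escalation gives more chances to notice a brief fall in pressure, and Section 2.3.1.2 expects mild and transient falls. Those extra chances increase with the cohort's target dose, so measurement intensity and dose move together.

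Randomization within cohort would deal with this. Placebo infants are masked and the MAP rule is written for study drug, so (by inference) each cohort's placebo infants follow the same schedule as its sildenafil infants. Pooling placebo gives up that match for the by-cohort columns. Cohort 1 sildenafil is then compared with infants who had more timed series on average, and Cohort 3 sildenafil with infants who had fewer. Part of any dose gradient could be a monitoring gradient, and Cohort 1 could look better and Cohort 3 worse than placebo for that reason. The by-cohort hypotension table is the trial's main statement on dose and safety.

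**Working it through.** **The plan's own figures.** The plan gives no figure for monitoring intensity. Its nearest figures on hypotension, in Section 12.2, reproduce: at a rate of 0.05 the chance of at least one event is 1 − 0.95^30 = 0.785 and 1 − 0.95^90 = 0.990 (stated: 78% and 99%). The 0.05 illustrates that calculation; Table 8 uses 0.1 to 0.3.

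**Timed series per fully escalated infant** (first dose plus increases in Table 4):
- Cohort 1: 1 + 1 = 2. Cohort 2: 1 + 3 = 4. Cohort 3: 1 + 6 = 7.
- Cohort 3 to Cohort 1: 7/2 = 3.5.
- Pooled placebo: (10×2 + 10×4 + 10×7)/30 = 4.33.
- All sildenafil: (30×2 + 30×4 + 30×7)/90 = 4.33. The overall comparison is therefore balanced on series; only the by-cohort columns are not.

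**Readings per series** (Section 4.2):
- IV: 3 before + 1 at start + 4 during the 60-minute infusion + 1 at end of flush + 2 + 4 hourly + 1 = 16, or 15 to 17 depending on how infusion and flush are counted.
- Enteral: 3 + 1 + 6 + 2 + 4 + 1 = 17.

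**All protocol-required MAP records over 28 treatment days:**
- Low count (15 per series, daily value only on days without a series): Cohort 1, 2×15 + 26 = 56; Cohort 3, 7×15 + 21 = 126; ratio 2.25.
- High count (17 per series, daily value on all 28 days): 2×17 + 28 = 62; 7×17 + 28 = 147; ratio 2.37.
- Adding 5 follow-up values in each cohort and 1 weaning value in Cohort 3: 132/61 = 2.16 to 153/67 = 2.28.

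**Share of treatment time.** At 8 hours per series and 28×24 = 672 hours, timed windows cover 16/672 = 2.4% in Cohort 1, 32/672 = 4.8% in Cohort 2 and 56/672 = 8.3% in Cohort 3.

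**Effect on detected hypotension.** The documents give no detection rate, so both models below rest on assumptions.

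*Model A: each series adds a chance p of a treated event regardless of drug.* Incidence from k series alone is 1 − (1 − p)^k; pooled placebo is the mean over cohorts.

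| p | Cohort 1 | Cohort 2 | Cohort 3 | Pooled placebo |
|---|---|---|---|---|
| 0.5% | 1.0% | 2.0% | 3.4% | 2.1% |
| 1% | 2.0% | 3.9% | 6.8% | 4.2% |
| 2% | 4.0% | 7.8% | 13.2% | 8.3% |

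With a 5% background and p = 1%, 1 − 0.95×0.99^k gives 6.9%, 8.7% and 11.5%, with pooled placebo at their mean, 9.0%.

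*Model B: events fall evenly over the 28 days, timed windows catch all of theirs, and routine care catches a share s of the rest.* With f the share of time in windows, detection is s + (1 − s)f. The Cohort 3 to Cohort 1 ratio is 3.50 at s = 0, 1.17 at s = 0.25 (0.3125/0.2679), 1.06 at s = 0.5, 1.02 at s = 0.75 and 1.00 at s = 1.

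**The case against.** The strongest reply is that the endpoint is not a MAP reading. It needs a physician's decision to treat. Section 9.1 monitors for it in every cohort from consent to 28 days after the last dose, and Section 9.4 accepts events found by examination, laboratory findings, MAP or other means. These are NICU inpatients on ventilation or CPAP. A daily lowest value presupposes several readings, and Section 8.1 allows continuous arterial measurement. If routine care already finds the events that get treated, extra timed readings add little, as Model B shows.

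Most of that stands, and it rules out three stronger readings.
- A reader might infer that detected hypotension must rise with cohort by design. The documents support only that it can.
- A reader might infer that Cohort 3 infants are searched 3.5 times as often. That ratio holds for timed series only; for all required MAP records it is about 2.2 to 2.4. The counts 2, 4 and 7 are also maxima, because Section 6.1 makes escalation conditional on respiratory support and liver enzymes.
- A reader might infer that a dose gradient should be claimed only if it persists in comparably monitored time. The plan gives no ground for that rule, and it would do harm: the restricted analysis drops the windows in which the higher doses of Cohorts 2 and 3 are first given, where a true acute effect would be expected to appear.

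It is also fair that the plan is descriptive, with no dose-trend test for hypotension, and that Section 12.4 refers to a separate statistical analysis plan, not among the documents reviewed, which could carry the remedy. None of this restores the within-cohort match lost by pooling, and nothing in the text reviewed lets a reader of the results judge how much monitoring contributed.

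**Conclusion.** The concern holds as a possible detection bias of unknown size. What is certain is the structure: up to 2, 4 and 7 timed series by cohort, an average of 4.33 in pooled placebo, an endpoint that depends on someone noticing and treating, and no planned display or analysis that addresses it. The bias, if present, would favour Cohort 1 and count against Cohort 3 relative to pooled placebo. Sildenafil overall against pooled placebo is not affected in this way, provided that both arms escalate alike.

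The size ranges from material to negligible. An assumed 1% per series gives 2.0%, 3.9% and 6.8% from the series alone; routine care that finds a quarter or more of the events outside the windows leaves a Cohort 3 to Cohort 1 ratio of 1.0 to 1.2. The documents cannot settle which applies. This warrants a cheap improvement to the analysis plan; it does not show that the primary result will be wrong.

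**What to change.** Amend Section 12.4, or the separate analysis plan, as follows. No change to the MAP schedule is proposed.

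1. Keep all-event hypotension incidence as the primary result.
2. Beside the pooled placebo column, show hypotension for each cohort's concurrent placebo infants.
3. As a supportive companion, report events with onset inside and outside a protocol-timed MAP window, by cohort and arm. Use onset time if it is captured; otherwise classify by whether onset fell on a first-dose or escalation day.
4. Report the number of timed series per infant by cohort and arm, since actual counts may fall below 2, 4 and 7.
5. State that any dose gradient will be interpreted in light of items 2 to 4, and that a dose-related safety signal will be reported whether or not the companion analysis agrees.

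**Cost.** Mostly wording and one derived flag. Dose times are already recorded (Section 4.2, item 2), but Section 9.2.6 mentions only a start date for SAEs and ESIs, and the fields listed in Section 9.4 include no onset time, so one eCRF field may be needed. The day-based fallback is coarser, because a day holds up to three doses.

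**Limit.** Ten placebo infants per cohort give little precision. For 1 event in 10, the Wilson 95% interval has centre (0.1 + 3.84/20)/(1 + 3.84/10) = 0.211 and half-width 1.96×√(0.1×0.9/10 + 3.84/400)/(1 + 3.84/10) = 0.193, so it runs from about 0.02 to 0.40. The concurrent column therefore supplements the pooled one and does not replace it.

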4.3 Weaning Period (Cohorts 2 and 3)

The weaning period will begin following Day 28 of study drug or, following the last day of study drug if participant was withdrawn from study drug prior to Day 28 and the dose escalated to \geq 0.5 mg/kg IV or \geq 1 mg/kg enteral.

The following information will be collected and recorded while the participant is weaning from study drug:

1. Date, time, amount and route of study drug dose
2. MAP (the lowest MAP value on last day of wean should be recorded).
3. Respiratory assessment, daily (Section 8.2.2.3)

-
4. Concomitant medications of special interest (Section 6.5.1)
 5. Echocardiogram and cardiac catheterization reports, if performed per local standard of care
 6. Adverse events (Section 9.3)

4.4 Follow-up Period

The follow-up period will include Days 1-28 after the last study drug dose; last study drug dose may occur prior to Day 28 for those participants who withdraw from study drug early; on Day 28 for those participants who complete the full treatment period; or after last weaning dose for those participants who require weaning. The following information will be reported in electronic data capture system (EDC) at Day 1 (+ 2 days) and 14 (\pm 2 days) of the follow-up period (or days closest to and after Day 1 and 14, if >1 assessment is available), except for MAP, AEs, and SAEs (which will be reported from Days 1-28 post last study drug dose) and standard of care echocardiograms or cardiac catheterization reports:

1. Physical examination, including actual weight
2. MAP (the lowest valid MAP value on follow-up Day 1, 7, 14, 21, and 28 should be recorded).
3. Respiratory assessment, daily (Section 8.2.2.3)
4. Laboratory evaluations obtained per local standard of care (Section 8.2)
5. Concomitant medications of special interest (Section 6.5.1)
6. Echocardiogram on follow-up Day 1 (+2 days). If performed per local standard of care, a study-specific echocardiogram need not be repeated. If not performed per local standard of care on Day 1 (+2 days) of the follow-up period, an echocardiogram will need to be performed.
7. Echocardiograms and cardiac catheterization reports, if performed per local standard of care (during follow-up Days 1-28)
8. Adverse events and SAEs (during follow-up Days 1-28 [Sections 9.3])

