3.2.2.2 Preliminary Effectiveness

The presence or absence of PH will be determined using central review by blinded pediatric cardiologists of echocardiograms performed at the end of the study period.

The developed population PK model will be linked to the diagnosis of PH made by echocardiography at the end of the study period to develop a population PK/PD model. We will use the model to simulate the effect of variable sildenafil exposures on the probability of developing PH.

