4.5 Final Study Assessment

Final study assessment will occur at the time of discharge or transfer. The following information will be collected:

1. Physical examination, including actual weight
2. Respiratory assessment (Section 8.2.2.3))
3. Concomitant medications of special interest (Section 6.5.1)
4. Echocardiogram and cardiac catheterization reports, if performed per local standard of care on the day of discharge or transfer or up to 2 days prior.
5. Global rank (Section 8.2.2.4)
6. Discharge information
 - A. Discharge or transfer
 - B. Death
 - C. Duration of hospitalization
7. Record if treatment for ROP was required

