⁸ Dosing may be adjusted according to any weight changes determined at baseline, study Days 7, 14, and 21.

⁹ Concomitant medications of special interest will be recorded during the entire study period.

¹⁰ AEs will be collected following informed consent through 28 days post last dose of study drug.

¹¹ If performed per local standard of care

¹² Transfer, discharge, duration of hospitalization or death; record if treatment for ROP was required.

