A multivariable mixed-effects model will be used to explore the relationship between the maximum and total dose of sildenafil and change in PH, death, and death or PH at 28 days of study drug and at the end of hospitalization or 52 weeks PMA, whichever comes first. We will use 52 weeks PMA because we found that 95% of infants with severe BPD died or were discharged home by this time.⁷

Planned sensitivity analyses of the primary endpoint

To address the potential effect of multiples enrolled in the study on the primary endpoint, we will conduct the following 2 sensitivity analyses:

- Sensitivity analysis #1 using only the first randomized sibling from any multiple gestations.
- Sensitivity analysis #2 using generalized estimating equations (GEE) with log link random effect for siblings to compute ratios of hypotension between the sildenafil and placebo groups.

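### Pulmonary hypertension is to be modelled at end of hospitalization or 52 weeks PMA, but no echocardiogram is required then, so the late result rests on scans that clinicians chose to order

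*Combined protocol and SAP*

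**What the plan says.** **What is to be analysed.** Section 12.4 (Preliminary Effectiveness) proposes a mixed-effects model whose stated purpose is this: "explore the relationship between the maximum and total dose of sildenafil and change in PH, death, and death or PH at 28 days". The full timing is "at 28 days of study drug and at the end of hospitalization or 52 weeks PMA, whichever comes first". Section 3.2.2.2 bases the presence of PH on central, blinded reading of "echocardiograms performed at the end of the study period", a label to which it attaches no date, and links the same diagnosis to the PK/PD model.

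**What is collected.** Section 4.4 requires one scan after baseline: "Echocardiogram on follow-up Day 1 (+2 days"). Follow-up is counted from the last dose, "or after last weaning dose for those participants who require weaning". Scans during treatment (Section 4.2), during weaning (Section 4.3) and in the rest of follow-up Days 1-28 (Section 4.4) are recorded only when local practice produces them. For the end of the stay, Section 4.5 says "Final study assessment will occur at the time of discharge or transfer" and takes an echo "if performed per local standard of care on the day of discharge or transfer or up to 2 days prior". Table 6 agrees: the footnote "If performed per local standard of care" is attached to the treatment, weaning and final-assessment echo cells but not to the follow-up cell. No echo or visit is set at 52 weeks PMA.

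**The concern.** Two modelled time points and one further label do not line up with the single required scan.

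The serious mismatch is at the later time point. After follow-up Day 28, the only echo that enters the database is one ordered locally within a three-day window around discharge or transfer. Clinicians are more likely to order that scan for an infant they suspect of having PH, so scanned infants would not represent the cohort. Dropping the unscanned infants pushes the PH rate up, and calling them PH-free pushes it down. The supplied text has no rule for them. An infant transferred elsewhere has its final assessment at transfer, which is not the end of its hospitalization.

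The PH data feed the PK/PD simulations, and Section 2.2 says that early studies should inform a pivotal efficacy trial. A late dose-PH estimate built on selected scans could be read as a formal result when it is not one.

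**Working it through.** **1. The protocol's own clock.** 28 treatment days + 6 weaning days (Table 5) = 34 drug days, and 34 + 28 follow-up days = 62. This matches the maximum participation stated in the Protocol Summary.

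**2. When the required echo falls (completers).** Echo day = last dose day + 1 to + 3.
- Cohort 1, no wean: 28 + 1 to 28 + 3 = study Day 29-31. This serves in effect as 28 days of study drug.
- Cohorts 2-3, after the wean: 34 + 1 to 34 + 3 = study Day 35-37. Section 6.1 weans placebo infants too, so this holds in both arms.
- Early stoppers are scanned earlier.

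**3. Interval with no echo except the discharge or transfer scan.** Follow-up Day 28 is study Day 28 + 28 = 56 (Cohort 1) or 34 + 28 = 62 (Cohorts 2-3). Take study Day 1 to fall at the entry PMA.

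| Entry PMA | Cohort | PMA at follow-up Day 28 | Days left to 52 0/7 |
|---|---|---|---|
| 32 0/7 | 1 | 39 6/7 | 85 |
| 32 0/7 | 2-3 | 40 5/7 | 79 |
| 44 6/7 | 1 | 52 5/7 | 0 |
| 44 6/7 | 2-3 | 53 4/7 | 0 |

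So the interval is 0 to 85 days in Cohort 1 and 0 to 79 days in Cohorts 2-3. Discharge may end it sooner.

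**4. Size of the selection at the late time point.** Assumptions: true PH 20% (Section 2.2 gives about 20% in severe BPD, with no time frame). The documents give no scan rates, so a range is used.
- Unscanned infants dropped, with r = scan rate in PH infants divided by scan rate in others. PH among scanned = 0.2r / (0.2r + 0.8). For r = 1.5: 0.3/1.1 = 27%. For r = 2: 0.4/1.2 = 33%. For r = 3: 0.6/1.4 = 43%.
- Unscanned infants counted as PH-free. Observed PH = 0.2 × the proportion of PH infants scanned: 0.2 × 0.3 = 6% to 0.2 × 0.9 = 18%.

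**5. Effect of echo day at the required scan (completers, no drug effect).** Assume PH by day d is 1 - 0.8^(d/29), so 20.0% by Day 29 and 23.6% by Day 35. Total IV doses from Tables 4 and 5, three doses a day with the wean included, are 40.5, 84.0 and 148.5 mg/kg for Cohorts 1 to 3, and 0 for placebo. The fit is a one-echo logistic model on total dose with 30 sildenafil and 10 placebo infants per cohort, a simplified stand-in for the planned mixed-effects model.
- OR for 148.5 versus 0 mg/kg: 1.14, SE 0.589. The 95% CI factor is exp(1.96 × 0.589) = 3.2 each way.
- With echo day added: OR 1.00, SE 0.666. The SE ratio is 0.666/0.589 = 1.13.

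**6. Does a common echo day cure PH-related early stopping?** Let 20% of both arms stop early, scan everyone on Day 29, set PH at 25%, 35% or 50% in stoppers and 20% in the rest. The total-dose OR is 0.87, 0.66 or 0.46 for stopping on Day 5, and 0.91, 0.76 or 0.60 for Day 14. The distortion remains although echo timing is identical for all, so it does not come from the echo schedule.

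**The case against.** **The details may be in a separate SAP.** Section 12.4 defers to a separate statistical analysis plan and a separate PK plan, neither of which is in the supplied text. Windows and missing-echo rules could be there. This stands as far as rules go, but no analysis plan can supply scans that were never collected.

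**Other PH information is collected.** Standard-of-care echoes in follow-up Days 1-28 are recorded, and Section 6.5.1 records sildenafil, bosentan, epoprostenol and inhaled nitric oxide for the entire study period. Catheterization reports and clinical diagnoses are also kept. These help to describe late PH, but Section 3.2.2.2 defines PH by centrally read echo.

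**Few infants reach 52 weeks PMA in hospital.** Section 12.4 cites 95% dead or discharged home by then. This stands: the missing 52-week scan matters for few infants, and the discharge scan is the main gap.

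**Tempting stronger readings.** A reader might infer that echo timing seriously distorts the dose-PH estimate at the required scan. The figures do not support that: among completers the OR is 1.14 against a CI factor of 3.2. A reader might also blame the echo schedule for bias from infants who stop because they are developing PH. Step 6 shows that a common echo day leaves that bias in place. It arises because total dose is a post-randomisation exposure, which is a separate issue. Nor is the 28-day label wrong for everyone, since Day 29-31 serves it well enough in Cohort 1 completers.

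**The remedy loses something.** Section 2.2 says that most BPD-related PH appears later in life, so giving up the formal late PH analysis has a price. That stands, but a formal model on selected scans would not answer the late question reliably either.

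**Conclusion.** The concern holds for the late time point. PH, and death or PH, at end of hospitalization or 52 weeks PMA cannot be estimated reliably from the scans the protocol collects. Under the assumptions in step 4, a true 20% could appear as anything from 6% to 43%, depending on who is scanned and how the rest are counted. The 20% and the scan rates are assumptions, and actual ordering practice could make the error smaller or larger.

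At the required echo the problem is mainly one of labels: Sections 3.2.2.2, 4.4 and 12.4 describe the PH assessment time in three different ways, and in Cohorts 2-3 the scan follows the wean. The effect on the dose estimate among completers is small.

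This is an exploratory secondary analysis. The primary hypotension endpoint is unaffected, and the death component needs no echo. The change is worth making because it is cheap and prevents a selection-biased model result from being presented as formal.

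**What to change.** - **(a) One definition.** For the dose models and the PK/PD model, define PH, and death or PH, on the required, centrally read follow-up Day 1 (+2 days) echo. Use that one label in Sections 3.2.2.2, 4.4 and 12.4.
- **(b) Late time point.** Do not present PH or death-or-PH at end of hospitalization or 52 weeks PMA as a formal dose-response result. Report PH descriptively among infants with an echo, giving the numbers scanned, unscanned and transferred in each arm. Keep death as the modelled outcome.
- **(c) Sensitivity analysis only.** Add days from first dose to echo to the model at the required scan. State that this variable is post-randomisation and that adjusting for it does not remove bias from informative stopping.
- **(d) Separate reconciliation.** Section 5.5.1 sends infants suspended for more than 48 hours directly into follow-up, whereas Sections 4.3 and 6.1 wean withdrawn infants in Cohorts 2-3 whose dose has reached the stated threshold. For those infants the choice moves the required echo by at least 6 days. The passages must be reconciled, and no view is taken here on which is right.

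**Cost.** SAP wording and a short protocol clarification, with no added echo or burden on infants. The formal late PH analysis is lost and later-onset PH is only described. Death alone is sparse: at an assumed 5% to 10% there would be 6 to 12 deaths in 120, and the same logistic fit gives a 95% CI factor for the dose OR of about 9 down to 5 each way. The dose standard error is about 13% larger in the echo-day model among completers.
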